5.2.7. Analysis of secondary variables

The following analyses will be performed according to secondary objectives.

1) To estimate the QoL of patients with IPF according to predicted FVC% through the SGRQ and EQ-5D-5L questionnaires and the Barthel index

Health-related quality of life (QoL) will be investigated with the St George's Respiratory Questionnaire (SGRQ) and the EQ-5D-5L questionnaire. Quality of life will be assessed at visits T0, T6 and T12.

The **St. George's Respiratory Questionnaire (SGRQ)** is a 50-item questionnaire developed to quantify the impact of the disease on the health and QoL perceived by patients with respiratory diseases. It consists of 50 items divided into 3 scales: symptoms (frequency and severity of respiratory symptoms), activity (activity limitations due to dyspnoea) and impact (psychological and social functioning disorders caused by the disease). The final scores range from 0 (fewest limitations) to 100 (most limitations). Spanish validated version will be used.

For the **SGRQ**: mean, SD, 95% CI of the mean, median, IQR (P25-P75), max. and min. will be calculated from the scores obtained on the three scales (symptoms, activity, impact) and from the total score in the total population and in each subpopulation (FVC <50%, FVC 50-80%, FVC >80%).

The **EQ-5D-5L** consists of a questionnaire and a visual analogue scale (EQ-VAS). The EQVAS is a self-rated health status using a VAS (0-100). The EQ-VAS records the subject's perceptions of their own current overall health. The self-assessment questionnaire is self-reported description of the subject's current health in 5 dimensions i.e., mobility, self-care, usual activities, pain/discomfort and anxiety/depression. The subject is asked to grade their own

current level of function in each dimension into one of five degrees of disability (no problems, slight problems, moderate problems, severe problems, and extreme problems).

This decision results in a 1-digit number expressing the level selected for that dimension. The digits for 5 dimensions can be combined in a 5-digit number describing the respondent's health state. Spanish validated version will be used.

For the **EQ-5D-5L questionnaire**: as the data are not continuous but ordinal, the information will be presented in terms of absolute and relative frequencies for each subpopulation (FVC <50%, FVC 50-80%, FVC >80%) by levels in each dimension. The EQ-5D-5L comprises the following 5 dimensions: mobility, self-care, usual activities, pain/discomfort and anxiety/depression. Each dimension has 5 five degrees of disability (no problems, slight problems, moderate problems, severe problems, and extreme problems).

Barthel Index will be used to score the ability of a patient to care for himself. It consists of 10 items, the values assigned to each item are based on time and amount of actual physical assistance required if a patient is unable to perform the activity. The final score range from 0 and 100. Patient scoring 100 is continent, feeds himself, dresses himself, gets up out of bed and chairs, bathes himself, walks at least a block, and can ascend and descend stairs. Spanish validated version will be used.

For the **Barthel index**: the items will be presented in terms of absolute and relative frequencies for each subpopulation (FVC <50%, FVC 50-80%, FVC >80%). The final score (0-100) will be presented by mean, SD, 95% CI of the mean, median, IQR (P25-P75), max. and min. will be calculated in each subpopulation (FVC <50%, FVC 50-80%, FVC >80%).

b) To explore the determinants of costs and QoL in patients with IPF according to predicted FVC%

In order to explore the determinants of costs and QoL in patients with IPF according to predicted FVC%, the following variables will be collected in the CRF at visit T0, T6 and/or T12:

- Sociodemographic variables: age, gender, employment, net incomes (T0).
- Anthropometric variables: weight, height and BMI (T0).
- Characteristics of IPF: time of IPF diagnosis (T0), FVC (L) (T0, T6, T12), FVC % predicted (T0, T6 and T12), FVC rate change by year (T0 and T12), DLCO (T0, T6 and T12), the

Barthel Index (T0, T6 and T12), 6MWD (T0 and T12), concomitant diseases related to IPF (T0, T6 and T12), pharmacological and non-pharmacological treatments related to IPF (T0, T6 and T12).

- Smoking status (T0, T6 and T12).
- Work with animals (now or in the past) (T0)
- Use of formal and/or informal caregiver (T0, T6 and T12).

If sample size allows, bivariate exploratory methods e.g. analysis of variance (ANOVA), Kruskal-Wallis test, Pearson/Spearman correlation will also be applied to explore predictors of costs and quality of life for each study subpopulation (FVC <50%, FVC 50-80%, FVC >80%) such as sociodemographic and clinical variables collected.

Taking into account that the expected final number of patients of the FVC <50% stratum could be small, with less of 20 patients, and the limitations that a multivariate analysis might have, an exploratory bivariate analysis could be performed with those variables considered as relevant.

Some variables may be categorised to provide practical information in the clinical setting.

If sample size allows, multivariate exploratory analyses (e.g. generalized linear models) will be applied which include costs and quality of life as dependent variables, and the explanatory variables will be discussed based on previous bivariate analyses and clinical relevance (with a $p < 0.1$). Sample size and constraints imposed by the analysis models may prevent to include all variables of interest in this setting.

c) To characterize acute IPF exacerbations (frequency and cost) according to FVC% predicted level

In order to characterize acute IPF exacerbations during one year according to FVC% predicted level at one year, the following variables will be collected in the eCRF along the study (12 months).

- Acute exacerbation related resource use for direct cost estimation: primary and secondary care visits, emergency visits (primary care and hospital), hospitalizations, ICU with and without intubation (qualitative analysis), outpatient tests and other examinations, use of transport, use of formal caregiver, pharmacological and non-

pharmacological treatments (except treatments administered in hospitalization), orthopaedic material, formal social services, economic aid and structural adaptations.

- Acute exacerbation related resource use for indirect cost estimation: patients' days off work and informal caregiver.

- Costs will be quantified as explained in section 5.2.3.

The total number of acute IPF-related exacerbations, as well as the use of resources and costs associated with the events during one year according to the predicted FVC at the time of inclusion (FVC <50%, FVC 50-80%, FVC >80%) will be described.

For the quantitative (continuous) variables, the mean, the SD, the 95% CI of the mean, the median, IQR, min and max will be calculated. Qualitative (categorical) variables will be presented as absolute and relative frequencies (percentages).

d) To describe the cost and QoL variation associated with the lung capacity deterioration (change among the FVC % predicted level along 12 month)

In order to estimate the direct and indirect costs according to FVC deterioration the following variable will be collected in the eCRF along the study (T0, T6 and T12):

- FVC % predicted along the study (T0, T6 and T12)
 - Men: $FVC\% \text{ predicted } (\%) = 100 \text{ FVC} / (0,0678 \text{ T} - 0,0147 \text{ E} - 6.0548)$
 - Women: $FVC\% \text{ predicted } (\%) = 100 \text{ FVC} / (0,0454 \text{ T} - 0,0211 \text{ E} - 2.8253)$
 - (FVC is FVC in liters, T is height in cm and E is age in years)

The calculated variable will be stratified into the following subgroups between T0 and T12:

- $\leq -10\%$
- from -10% to -5%
- $> -5\%$

Descriptive analyses will be carried out of direct and indirect costs and patient quality of life according to the change in FVC (<-10%, from -10% to -5%, and >-5%) between T0 and T12.

For the quantitative (continuous) variables, the mean, the 95% CI, the median, IQR, min and max will be calculated. Qualitative (categorical) variables will be presented as absolute and relative frequencies (percentages).

When sample size is minimum, subgroup analyses will be explored for the following subgroup variables:

- % FVC predicted in T0 (FVC <50%, FVC 50-80%, FVC >80%)
- antifibrotic treatment vs. non antifibrotic treatment during study period
- one acute IPF exacerbation vs. more than one acute IPF exacerbation during study period

e) To assess the QoL of the caregiver through the Zarit Burden Interview questionnaire

Caregiver quality of life will be explored using the Zarit questionnaire. Caregiver quality of life will be assessed at visits T0, T6 and T12.

Caregivers who have signed the specific written informed consent form will be asked to complete the Zarit Burden Interview. It is a self-report measure. The revised version contains 22 items. Each item on the interview is a statement which the caregiver is asked to endorse using a 5-point scale. Response options, in the spanish version, range from 0 (Never) to 4 (Nearly Always). The final scores range from 0 and 88: Little or no burden (≤ 42), mild to moderate burden (22-40), moderate to severe burden (41-60) and severe burden (≥ 61).

The responses to the 22 items that make up the instrument will be reported, as well as the total score for the questionnaire. The distribution of caregiver burden will be described by means of absolute and relative frequencies (percentages), according to the following categories:

- Little or no burden: Zarit score ≤ 21
- Mild to moderate burden: Zarit score > 21 and ≤ 40
- Moderate to severe burden: Zarit score > 40 and ≤ 60
- Severe burden: Zarit score ≥ 61

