## **7. RATIONALE AND BACKGROUND**

IPF is defined as a specific form of chronic, progressive fibrosing interstitial pneumonia of unknown cause, occurring primarily in older adults, limited to the lungs, and associated with the histopathologic and/or radiologic pattern of UIP (1). FVC is a reliable, valid, and responsive measure of disease status in patients with Idiopathic Pulmonary Fibrosis (8).

There are no large-scale studies of the incidence or prevalence of IPF on which to base formal estimates. Prevalence estimates for IPF have varied from 2 to 29 cases per 100,000 in the general population (9, 10, 11, 12, 13). The wide range in these numbers is likely explained by the previous lack of uniform definition used in identifying cases of IPF, as well as by differences in study designs and populations (1). It is estimated that IPF affects about 7,500 people in Spain (14), however prevalence and incidence for IPF in Spain has not been studied and is uncertain.

On the other hand there is no evidence on the cost of patients with IPF in Spain based on actual clinical practice. The only study carried out in Spain is based on Delphi panels and concluded that the management of patients with IPF in Spain, especially patients with rapid disease progression, has a high economic impact on the NHS. In that study the parameter that varied the annual cost per patient the most was the resource use associated with acute exacerbations (2). Nevertheless the study did not provide any information on the burden of disease by level of severity or from the societal perspective, nor took into account pharmacological costs as pirfenidone had not been reimbursed and was only available through compassionate use when the analysis was performed.

The cost associated with acute exacerbations represents nearly half of the total cost of managing patients with IPF (2). Therefore, considering that low forced vital capacity (FVC) has proven the most consistent risk factor for acute exacerbation of IPF (3) is expected that patients with low FVC (FVC < 50%) have higher cost. Furthermore, the recent introduction of new antifibrotic agents (nintedanib, pirfenidone) changed the therapeutic strategy, so did the total cost of the disease.

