4.2. SAMPLE SIZE JUSTIFICATION

In view of the lack of Spanish studies that analyse the economic impact of IPF according to deterioration in the predicted FVC, and as this is a prospective observational study, it was decided to observe all the patients with IPF that meet the inclusion/exclusion criteria during the inclusion period. Based on the investigation into the viability of recruitment, we expect to include approximately 200 patients.

The primary objective of the study is to compare the economic impact of IPF according to FVC levels. This would mean opting for a balanced sample size for the three comparison groups.

However, knowing the approximate patient prevalence according to predicted FVC (5-11% predicted FVC $<50\%$, 51-73% predicted FVC 50-80%, and 22-38% predicted FVC $>80\%$) and the sponsor's internal data, we have estimated to find:

- 10-22 patients with predicted FVC $<50\%$.
- 102-143 patients with predicted FVC 50-80%.
- 43-76 patients with predicted FVC $>80\%$.

Depending on the final distribution obtained in terms of number of patients for each comparison group and given the exploratory nature of this study, it is expected that comparisons between some groups will have a descriptive approach, although the expected comparison analyses will be carried out as stated in this protocol (explorative statistical model if sample size allows). Although the expected number of patients with predicted FVC $<50\%$ is

small, it should at least provide first insights into the costs within this patient subgroup. In view of the lack of previous data on the cost of the disease according to the study's primary endpoint in Spain, this will be the first Spanish cost comparison study according to predicted FVC.

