5.2.9. Handling of missing data

Missing values will not be imputed in the main analysis. However, if considering only observed values for an analysis is felt to bias the results post-hoc sensitivity analyses including imputation techniques might be applied.

For each questionnaire, its indications will be followed (for example, calculating the score considering the number of available items or missing all data). A missing response in either of the questionnaires will exclude the patient from the specific analyses.

In context of concomitant medication date in T0, missing data in the month will be imputed as June.

In context of pharmacological and non-pharmacological treatment related to FPI, if the initial treatment date is missing and the treatment is ongoing, the cost corresponding to a full year will be imputed (in case the diagnosis of the PFI is earlier than 2018).

No other missing data will be imputed. If patients have missing values for any other endpoints, these patients will be excluded from the analysis of that endpoint.

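### Exacerbation frequency by baseline FVC stratum has no patient-time denominator and no rule for patients who die or leave before T12

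*SAP*

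**What the plan says.** SAP 3.2 sets the objective: the frequency and cost of acute exacerbations over one year, by FVC % predicted at baseline. SAP 5.2.7 c) carries it out by describing "The total number of acute IPF-related exacerbations, as well as the use of resources and costs associated with the events during one year" by FVC group at inclusion. (The lead-in to that subsection speaks of FVC level at one year. I take the inclusion value, which matches the objective; the two phrases should be reconciled.)

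Generic summaries follow directly: "For the quantitative (continuous) variables, the mean, the SD, the 95% CI of the mean, the median, IQR, min and max will be calculated", and "Qualitative (categorical) variables will be presented as absolute and relative frequencies (percentages"). Protocol 9.7.2 c) is equivalent in substance.

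The other relevant provisions are:

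- **Standardisation to a year.** SAP 5.2.8 expresses costs per patient and per year. No such statement covers exacerbations.
- **Missing data.** SAP 5.2.9 says "If patients have missing values for any other endpoints, these patients will be excluded from the analysis of that endpoint". It does not mention death or partial follow-up.
- **Analysis set.** SAP 5.2.2 treats patients with resource-use data as valid for the main analysis. The Protocol 9.2.3 flow chart collects those data at T6 and T12.
- **Loss to follow-up.** Protocol 9.9 names it as a source of selection bias and gives no rate.
- **Stratum sizes.** SAP 4.2 expects "10-22 patients with predicted FVC $<50"%, "102-143 patients with predicted FVC 50-80"%, and 43-76 above 80%.

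**The concern.** A one-year frequency needs a denominator. A count or a mean per enrolled patient gives a patient who leaves at month 3 the same weight as one observed for the full year, although only a quarter of the year was at risk. Completers vary too, because the T12 window of plus or minus one month makes observed time 11 to 13 months.

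The gap matters because of the study's own rationale. Protocol 7 states that "low forced vital capacity (FVC) has proven the most consistent risk factor for acute exacerbation of IPF (3"), and expects higher cost in FVC <50% for that reason. If early exit is also more common in that stratum, a measure that ignores time at risk shrinks the very contrast the objective is meant to show. If patients who die were handled as missing, their exacerbations, including fatal ones, would leave the count altogether. Protocol 9.3.2.2 also names the number of exacerbations as a candidate determinant of cost and QoL, so the variable is used more than once.

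**Working it through.** **1. The plan's own figures.** SAP 4.2 says "we expect to include approximately 200 patients". Multiplying 200 by the stated prevalence limits:

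- FVC <50%: 200 × 5% to 11% = 10 to 22 (stated 10-22)
- FVC 50-80%: 200 × 51% to 73% = 102 to 146 (stated 102-143)
- FVC >80%: 200 × 22% to 38% = 44 to 76 (stated 43-76)

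The stated sizes reproduce closely. They are the only figures in the documents that bear on this point. Every rate and loss below is an assumption.

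**2. Totals.** Expected events = rate × n. At an assumed common rate of 0.2 per patient-year with full follow-up, the three strata give 2.0-4.4, 20.4-28.6 and 8.6-15.2 events. The middle stratum would show 102/22 = 4.6 to 143/10 = 14.3 times as many events as FVC <50% from size alone. Totals cannot be compared, but a mean per patient or a percentage removes this problem.

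**3. Mean per enrolled patient.** Mean events = rate × mean patient-time. With a constant hazard of exit and a one-year loss m, mean patient-time in years is m / (−ln(1 − m)).

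| One-year loss m | Mean patient-time | Mean falls below rate by |
|---|---|---|
| 5% | 0.975 | 2.5% |
| 10% | 0.949 | 5.1% |
| 20% | 0.896 | 10.4% |
| 30% | 0.841 | 15.9% |
| 40% | 0.783 | 21.7% |

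**4. Contrast between strata.** Apparent ratio = true ratio × (patient-time in FVC <50%) / (patient-time in FVC >80%). Take a true rate ratio of 2 and a 5% loss in FVC >80%:

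- 10% loss in FVC <50%: 2 × 0.949/0.975 = 1.95
- 20%: 2 × 0.896/0.975 = 1.84
- 30%: 2 × 0.841/0.975 = 1.73
- 40%: 2 × 0.783/0.975 = 1.61

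With equal losses the ratio stays at 2.0.

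**5. If patients who die were left out.** Assume a true rate of 0.30 per year, other deaths at a hazard of 0.1 per year, and a fraction c of exacerbations fatal. Survivors have only non-fatal events, so their mean is 0.30 × (1 − c). The mean over all enrolled patients is 0.30 × (1 − exp(−h))/h, with h = 0.1 + 0.30c.

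| Fatal fraction c | Survivors only | All enrolled, no patient-time | Events per patient-year |
|---|---|---|---|
| 0 | 0.30 | 0.286 | 0.30 |
| 0.3 | 0.21 | 0.273 | 0.30 |
| 0.5 | 0.15 | 0.265 | 0.30 |

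Exclusion does no harm when death is unrelated to exacerbation, and considerable harm when it is related. Events per patient-year recovers the rate in every row.

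**The case against.** Four arguments on the other side deserve an answer.

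- **Unequal stratum size.** A reader who stops at the sentence on totals might infer that the strata cannot be compared because their sizes differ. The sentences that follow plan means, CIs and percentages, and these remove stratum size. The objection stands, and size is not the point here.
- **Direction of the error.** A reader might also infer that frequency in FVC <50% is understated as a matter of fact. The documents give no deaths, withdrawals or exacerbation rates by stratum. The between-stratum statement must remain conditional on differential exit.
- **Dropping deaths.** SAP 5.2.9 excludes missing values, and exacerbations are recorded along the study. A patient who dies at month 3 has an observed count, and SAP 5.2.2 does not require T12 completion. The survivors-only figures therefore show what one possible reading would cost; the plan does not direct it. What remains is that the text is silent, and a patient who dies before T6 could be removed under either section.
- **Precision and status.** The objective is described and not tested, and the smallest stratum is meant only to give first insights. With 6 events in 15 patient-years, an exact Poisson 95% interval runs from about 2.2 to 13.1 events, or 0.15 to 0.87 per year. That is wider than the bias in step 3. This limits the importance of the point, but it does not justify leaving the denominator undefined.

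The determinants analysis is a weaker route to harm than it first appears. It is run within each stratum, and the multivariate QoL outcome is the T0 value.

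**Conclusion.** The point holds in conditional form. Neither document gives exacerbation frequency a patient-time denominator or a rule for early exit. The planned per-patient mean will lie below the true rate wherever follow-up is cut short, by about 5% to 22% at an assumed 10% to 40% one-year loss under a constant exit hazard. The contrast between strata is distorted only if exit differs by stratum: a true ratio of 2 would read as 1.95 to 1.61 under the losses in step 4. It could be distorted further if patients who die were treated as missing and some exacerbations are fatal. This is a worthwhile, low-cost improvement to a descriptive secondary objective. It does not affect the validity of the study as a whole.

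**What to change.** In SAP 5.2.7 c), report for each T0 FVC stratum:

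- the number of exacerbations after T0 (the flow chart also marks exacerbations at T0, so the start of the window needs stating);
- patients with at least one event, n and %;
- patient-years from T0 to T12, death or withdrawal;
- events per patient-year with an exact Poisson 95% CI. Use a negative binomial model with a log follow-up offset only if numbers allow, since the Poisson interval is too narrow when events cluster within patients.

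State that every evaluable patient contributes events, including fatal ones, and time until exit. State also that early exit is not a missing value for this endpoint under 5.2.9, and that lack of a T6 or T12 resource-use record does not remove the patient from this description. Keep totals as supporting information.

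The inputs are already collected: exacerbations (Protocol 9.2.3), discontinuation dates (Protocol 9.2.4) and fatal adverse events (Protocol 11.2). Censoring at lung transplantation is optional. It is an additional analytic choice and needs a transplant date, which the flow chart does not show as a separate item.

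The cost is SAP wording and one derived follow-up time per patient. The downside is visibly wide intervals in the stratum of 10 to 22 patients.

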#### **9.3.2.2     Secondary outcomes**

In order to estimate the QoL of patients with IPF according to predicted FVC% through the SGRQ and EQ-5D-5L questionnaires and the Barthel index.

- Health-related quality of life (QoL) will be investigated with the St George's Respiratory Questionnaire (SGRQ) and the EQ-5D-5L questionnaire. Quality of life will be assessed at visits T0, T6 and T12.

(See section [9.7.1](#))

In order to explore the determinants of costs and QoL in patients with IPF according to FVC % predicted level, the following variables will be collected in the CRF at visit T0 and T12:

- Sociodemographic variables: age, gender, employment, net incomes (T0).
- Anthropometric variables: weight, height and BMI (T0).
- Characteristics of IPF: date of IPF diagnosis (T0), FVC (ml) (T0, T6, T12), FVC % predicted (T0, T6 and T12), FVC rate change by year (T0 and T12), DLCO (T0, T6 and T12), the Barthel Index (T0, T6 and T12), 6MWD (T0 and T12), concomitant diseases

 Direct costs: cost incurred for medical products and services used for the prevention, detection, and treatment of a disease.

 Indirect costs: costs incurred from missing work which is loss of productivity

Proprietary confidential information © 2017 Boehringer Ingelheim International GmbH or one or more of its affiliated companies

related to IPF (T0, T6 and T12), pharmacological and non-pharmacological treatments related to IPF (T0, T6 and T12).

- Smoking status (T0, T6 and T12).
- Work with animals (now or in the past) (T0)
- Use of formal and/or informal caregiver (T0, T6 and T12).

The number of exacerbation (5) events observed during the study period will also be explored for the cost and QoL determinants.

In order to characterize acute IPF exacerbations (5) during one year according to FVC % predicted level at one year, the following variables will be collected in the eCRF along the study (12 months).

- Acute exacerbation related resource use: primary and secondary care visits, outpatient visits, emergency visits (primary care and hospital), hospitalizations, ICU with and without intubation, outpatient tests and other examinations, use of transport, use of formal and informal caregiver, pharmacological and non-pharmacological treatments (except treatments administered in hospitalization), orthopedic material, formal social services, economic aid and structural adaptations.
- Acute exacerbation related days off work

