The total number of acute IPF-related exacerbations as well as the use of resources and costs associated with the events during one year according to the predicted FVC at the time of inclusion (FVC <50%, FVC 50-80%, FVC >80%) will be described.

For the quantitative (continuous) variables, we will calculate the mean, the SD, the 95% CI of the mean, the median and the IQR. Qualitative (categorical) variables will be presented as absolute and relative frequencies (percentages).

d) To describe the cost and QoL variation associated with the lung capacity deterioration (change among the FVC % predicted level along 12 month)

Descriptive analyses will be carried out of direct and indirect costs and patient quality of life according to the change in FVC (<-10%, from -10% to -5%, and >-5%) between T0 and T12.

For the quantitative (continuous) variables, we will calculate the mean, the 95% CI, the median and the IQR. Qualitative (categorical) variables will be presented as absolute and relative frequencies (percentages).

When sample size is minimum, subgroup analyses will be explored for the following subgroup variables (or others, if deemed appropriate, defined in the SEAP):

- % FVC predicted in T0 (FVC >80%, FVC 50-80% and FVC <80%)
- antifibrotic treatment vs non antifibrotic treatment
- one acute IPF exacerbation vs. more than one acute IPF exacerbation during study period.

e) To assess the QoL of the caregiver through the Zarit Burden Interview questionnaire. Caregiver quality of life will be explored using the Zarit questionnaire. Caregiver quality of life will be assessed at visits T0, T6 and T12.

We will report the responses to the 22 items that make up the instrument, as well as the total score for the questionnaire. The distribution of caregiver burden will be described according to the following categories (17):

little or no burden	→ Zarit score $\leq 21$
Mild to moderate burden	→ Zarit score $> 21$ and $\leq 40$
Moderate to severe burden	→ Zarit score $> 40$ and $\leq 60$
Severe burden	→ Zarit score $\geq 61$

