1.11. STUDY POPULATION AND TOTAL NUMBER OF SUBJECTS

It is planned that data of approximately 200 IPF patients in Spain will be collected.

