5.2.4. Analysis of the primary variable

To compare the economic impact of IPF according to predicted FVC% (FVC<50%, FVC 50-80%, FVC>80%), in adult patients through the estimation of annual direct and indirect costs associated with the disease)

Annual direct and indirect IPF-related costs will be quantified for each patient over the follow-up period of 12 months from the societal perspective and National Health Service (NHS).

Direct and indirect costs will be quantified according to resource use and days of sick leave.

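### The exploratory exacerbation subgroup sets one event against more than one and has no level for patients with none, so it cannot compare patients with and without an exacerbation

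*SAP*

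**What the plan says.** SAP 5.2.7 d) describes costs and quality of life by change in FVC over 12 months. It then lists three further subgroup variables under the condition "When sample size is minimum, subgroup analyses will be explored for the following subgroup variables". The third is "one acute IPF exacerbation vs. more than one acute IPF exacerbation during study period". Protocol 9.7.2 d) has the same split, and it also allows other subgroups: "or others, if deemed appropriate, defined in the SEAP". The SAP adds none, and SAP 5.3 records no changes to the planned analyses.

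Three other places deal with exacerbations:

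- Protocol 7 gives the motivation: "The cost associated with acute exacerbations represents nearly half of the total cost of managing patients with IPF".
- SAP 5.2.7 c) will describe, by baseline FVC stratum, "The total number of acute IPF-related exacerbations, as well as the use of resources and costs associated with the events during one year".
- Protocol 9.3.2.2 says that the number of exacerbation "events observed during the study period will also be explored for the cost and QoL determinants". The variable list for that objective in SAP 5.2.7 b) does not include it.

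**The concern.** A subgroup variable should place every patient in exactly one level. In the SAP list, baseline FVC (three strata) and antifibrotic treatment (with or without) do so. The exacerbation variable does not, because a patient with no event in the year belongs to neither level.

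The reference group for asking what an exacerbation adds to a patient's annual cost, or takes from quality of life, is the patients who had none. The split as written can only compare single with repeated events, among patients who had at least one. The protocol treats exacerbations as a large part of the cost of the disease, so the with-or-without comparison is the one that many readers of the report would look for. Depending on how common exacerbations are, the contrast might also rest on few patients.

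**Working it through.** **Comparison of the sections.** The question is whether any planned analysis explicitly compares annual cost or quality of life between patients with and without an exacerbation.

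- SAP 5.2.7 d) and Protocol 9.7.2 d): one versus more than one. No.
- SAP 5.2.7 c): number of events, and the resource use and cost attached to them, by baseline FVC. This describes the events. It does not compare patients by exacerbation status.
- SAP 5.2.7 b): determinants of cost and quality of life. The exacerbation count is not on the list, although the general reference to collected clinical variables leaves room for it.
- Protocol 9.3.2.2: the exacerbation count is planned as a determinant, with no restriction to patients who had an event. This would serve, but the SAP does not carry it over by name.

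**Group sizes.** The plan gives no exacerbation rate and no expected size for this subgroup, so it has no figure on this point to reproduce.

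Inputs from the documents:
- N = 200: "It is planned that data of approximately 200 IPF patients in Spain will be collected" (SAP 1.11).
- One year per patient: "Annual direct and indirect IPF-related costs will be quantified for each patient over the follow-up period of 12 months" (SAP 5.2.4).

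Assumed inputs:
- mean rate r per patient-year
- full follow-up for all 200 patients
- Poisson counts, with a negative binomial (shape k) as a check on overdispersion

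Poisson: P(0) = exp(−r), P(1) = r·exp(−r), P(>1) = 1 − P(0) − P(1).

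Example at r = 0.2: P(0) = 0.81873, P(1) = 0.16375 and P(>1) = 0.01752. Multiplied by 200, these give 163.7, 32.7 and 3.5 patients.

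| Assumed r | None (outside the contrast) | One | More than one | Share outside |
|---|---|---|---|---|
| 0.1 | 181.0 | 18.1 | 0.9 | 90.5% |
| 0.2 | 163.7 | 32.7 | 3.5 | 81.9% |
| 0.3 | 148.2 | 44.4 | 7.4 | 74.1% |
| 0.5 | 121.3 | 60.7 | 18.0 | 60.7% |
| 1.0 | 73.6 | 73.6 | 52.8 | 36.8% |

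Negative binomial: P(0) = (k/(k+r))^k, P(1) = k·(r/(k+r))·P(0), and P(>1) is the remainder. The more-than-one group becomes:

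| Assumed r | k = 1 | k = 0.5 |
|---|---|---|
| 0.1 | 1.7 | 2.2 |
| 0.2 | 5.6 | 6.8 |
| 0.3 | 10.7 | 12.2 |
| 0.5 | 22.2 | 23.2 |

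**Thresholds (Poisson).** Patients with none are more than half of the cohort when exp(−r) > 0.5, that is, when r < ln 2 = 0.69. Solving 200·P(>1) = 5 and 200·P(>1) = 10 gives r of about 0.24 and 0.36, so the top group is below 5 or below 10 patients only under those rates.

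**Within FVC-change groups.** Section d) is organised by three FVC-change groups. With an equal split (assumed), the more-than-one group averages 3.5/3 = 1.2 patients per group at r = 0.2 and 18.0/3 = 6.0 at r = 0.5.

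**With a zero level.** None versus at least one keeps all 200 patients: 181 versus 19 at r = 0.1, 164 versus 36 at 0.2, 148 versus 52 at 0.3, and 121 versus 79 at 0.5.

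**The case against.** The strongest reply is that little depends on this line. The subgroup is exploratory and conditional on sample size. Patients without an exacerbation drop out of this one split only. They remain in the primary cost comparison, in the description by FVC change and in the total-sample costs. The argument in Protocol 7 concerns the cost attributable to exacerbations and the higher risk at low FVC. SAP 5.2.7 c) addresses that directly, because exacerbation resource use is recorded separately for the cost items. All of this stands, and it limits the severity.

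A reader might go further and infer that most of the cohort is excluded and that one arm is nearly empty. The documents do not support either as fact, because they give no exacerbation rate. The first needs a rate below about 0.69 per year and the second a rate below roughly 0.24 to 0.36 (both Poisson). Overdispersion makes the first easier to meet and, at rates of 0.1 to 0.5, enlarges the small arm. Nor can one conclude that the plan fails to address exacerbation cost, given section c) and Protocol 9.3.2.2.

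The reply does not remove the missing level. The sample-size condition does not repair it either, since the minimum is undefined. If the condition blocks the contrast, the SAP names no patient-level comparison by exacerbation status. If it allows the contrast, patients without an event are still left out.

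It is also fair to say that single versus repeated events is a legitimate contrast. That is a reason to add a level, not to discard the split.

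**Conclusion.** The point holds as a gap in the definition, and it is minor. In both documents the levels of the exacerbation subgroup do not divide the cohort, and the subgroup cannot compare annual cost or quality of life between patients with and without an exacerbation. This conclusion rests on the text alone and needs no assumed rate.

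The numerical consequence is conditional. Over assumed rates of 0.1 to 0.5 per patient-year (Poisson, N = 200, full follow-up), about 181 to 121 patients fall outside the contrast and about 1 to 18 are in the more-than-one group. At a rate of 1.0, patients with none would no longer be the majority under Poisson, and the top group would hold about 53. The primary analysis and SAP 5.2.7 c) are unaffected.

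**What to change.** 1. In SAP 5.2.7 d) and Protocol 9.7.2 d), define the subgroup levels as 0, 1 and more than 1 acute exacerbation during the study period. This keeps the planned single-versus-repeated contrast.
2. State that none versus at least one is the main contrast when the more-than-one group is small, and write into the SAP the number that counts as small. The present sample-size condition gives none.
3. Add the number of exacerbations to the determinant list in SAP 5.2.7 b), so that it matches Protocol 9.3.2.2.
4. Record the change in SAP 5.3.

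The cost is about one line per place. Exacerbations are already collected at all three visits (Protocol 9.2.3), so no new data are needed.
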